The airflow obstruction in this disease is generally persistent as well as progressive (Lapperre et al 2004). It has two clinical phases (stable phase and exacerbation phase), both of which are associated with inflammation (Barbu et al 2011). Independent risk factors for COPD are male gender, advanced age, low socioeconomic status, occupational exposure and cigarette smoking

(both active and passive) (Caballero 2008), reactivity of airways, occupational factors and air pollution (Reilly et al 2004).

Vitamin D is a steroid important in bone mineralization and calcium homeostasis. The prevalence of vitamin D deficiency has been increasing in the general population in recent decades. The majority of circulating 25-hydroxyvitamin D [25(OH)D] is derived from sun exposure with a limited dietary contribution. The increased prevalence of vitamin D deficiency is attributed to sun avoidance, indoor lifestyle, use of sunscreen, and decreased intake of vitamin D-containing foods (Reilly et al 2004). Because vitamin D is sequestered in adipose tissue, the increasing prevalence of obesity also increases the prevalence of vitamin D deficiency (Holick 2007).

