(Said and Abd-Einaeem 2015)

With history of –

- Chronic pulmonary diseases, like –
 - bronchial asthma
 - respiratory tract infection
 - bronchiectasis
 - pneumothorax
 - pleural effusion

tuberculosis

pulmonary fibrosis

pneumonectomy or pulmonary lobectomy

- Chronic liver disease
- Malignancy
- Systemic hypertension
- Thyrotoxicosis
- Chronic cardiac diseases, like –
 angina
 congestive heart failure
 myocardial infarction
 cardiac arrhythmia
 cardiomegaly
- Use of drugs known to affect vitamin D metabolism within 1 month prior to study,
 as,
 Anticonvulsants
 Glucocorticoids
 Calcium

With biochemical evidence of –

- Diabetes mellitus
- Renal insufficiency

All the criteria mentioned above will be scrutinized by taking history and clinical examination, except vitamin D₃ deficiency, diabetes mellitus and renal insufficiency, which will be diagnosed biochemically.

Principles Of Bangladesh Good Clinical Practice:

(Directoriate general of drug administration 2011)

Before conducting the study the researcher will follow all the principals of Bangladesh GCP ,written below:

1. Clinical trials should be conducted in accordance with the ethical principles that have their origin in the Declaration of Helsinki, and that are consistent with GCP and the applicable regulatory requirement(s).
2. Before a trial is initiated, foreseeable risks and inconveniences should be weighed against the anticipated benefit for the individual trial participant and society. A trial should be initiated and continued only if the anticipated benefits justify the risks.
3. The rights, safety, and well-being of the trial participants are the most important considerations and should prevail over interests of science and society.
4. The available nonclinical and clinical information on an investigational product should be adequate to support the proposed clinical trial.
5. Clinical trials should be scientifically sound, and described in a clear, detailed protocol.
- 6 . A trial should be conducted in compliance with the protocol that has received prior institutional review board (IRB)/independent ethics committee (IEC) approval/favorable opinion.
7. The medical care given to, and medical decisions made on behalf of, participants should always be the responsibility of a qualified physician or, when appropriate, of a qualified dentist.
8. Each individual involved in conducting a trial should be qualified by education, training, and experience to perform his or her respective task(s).

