Investigator has applied for formal Clinical trials through www.Clinicaltrials.gov and was granted permission to go on with the trial (Annexure II) .On the first day of enrollment, the objectives, nature, purpose and potential risk of all the procedures used for the study will be explained in detail to each subject, with a cordial attitude giving emphasis on the benefits he might obtain from this study. He will be encouraged for voluntary participation and will be allowed to withdraw himself from the study even after participation, whenever he felt uneasy. If he agreed to be enrolled in the study, an informed written consent will be taken in a prescribed form (Annexure - IV). Detailed family history, medical history and thorough physical examination of each patient will be done and all the information will be recorded in a standard data sheet (Annexure - V). Then all the patients will be requested to attend the Department of Physiology at 9 am (about 1 and 1/2 hours after his breakfast) on the day of biochemical and spirometric examination.

On the examination day, 5 ml of venous blood will be collected and taken to the Hematology laboratory as soon as possible for the estimation of serum 25-hydroxycholecalceferol, serum glucose 2 hours after breakfast and serum creatinine. After that his height and weight will be measured and the spirometric lung function test will be done by using a portable spirometer. After getting all the biochemical and spirometric reports the final selection will be done, according to the inclusion and exclusion criteria.

Subsequently, all the eligible patients will be randomly assigned to either 'Control' or 'Study' groups and will be thoroughly informed about the objectives and detailed study procedure, once again. Then the patients will be examined for the baseline value of all the study variables in Day 1.

Again after 90 days the study variables will be collected from same 46 patients.

CONFOUNDING VARIABLES:

- Age: >40 years (Heideri 2015)
- Socioeconomic condition: Middle class (Martineau et al 2015)
- Smoking status: (Janssens et al 2010)
 - Current smoker = with history of active smoking
 - Ex-smoker = with history of 0 – 8 quit year
 - Duration = for >30 pack years
- BMI: 25 – 29.9 kg/meter-sq (Janssens et al 2010)
COPD patients at moderate stage according to GOLD criteria with > 4 years duration (Rees et al 2013)
- Stable COPD patients (Mehrparver et al 2010)
- Vitamin D₃ deficient: 30 ng/ml (Vitamin D council 2017)

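### Serum calcium is measured on Day 1, but it is not a named screening test or eligibility limit, and no rule requires the result to be seen before vitamin D3 at 80,000 IU per week is started

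*Combined protocol and SAP*

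**What the plan says.** STUDY PROCEDURE gives the sequence. On the examination day blood is drawn "for the estimation of serum 25-hydroxycholecalceferol, serum glucose 2 hours after breakfast and serum creatinine", and spirometry is done. Next, "After getting all the biochemical and spirometric reports the final selection will be done, according to the inclusion and exclusion criteria". Random assignment follows, and after it: "Then the patients will be examined for the baseline value of all the study variables in Day 1".

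The Exclusion Criteria section says how eligibility is checked: "All the criteria mentioned above will be scrutinized by taking history and clinical examination". Three conditions are carved out of that rule and settled in the laboratory instead; the sentence ends "except vitamin D₃ deficiency, diabetes mellitus and renal insufficiency, which will be diagnosed biochemically". Calcium appears once in the criteria, as one of the drugs listed under "Use of drugs known to affect vitamin D metabolism within 1 month prior to study". That is a rule about recent medication, not a limit on serum calcium.

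STUDY VARIABLES lists ionic calcium and PTH among the hematological variables, with no threshold and no action. The text then turns to prescribing: standard COPD treatment for everyone, plus vitamin D3 at 80,000 IU per week for 90 days in the study group. All study variables are measured again on day 90. Contact in between is by telephone, home visit and hotline, and no blood test is named.

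Two general provisions also bear on the point. Ethical Implications promises management or referral if a test shows an abnormality. The seventh Good Clinical Practice principle says that the medical care of, and decisions for, "participants should always be the responsibility of a qualified physician".

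**The concern.** The protocol makes the link to calcium itself. Its Introduction says: "Vitamin D is a steroid important in bone mineralization and calcium homeostasis". It also plans to measure calcium, phosphate and PTH. Yet the calcium result has no stated role in deciding who is randomised or who is dosed.

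The stake is patient safety. A man whose calcium is already high could start a 90-day course of high-dose vitamin D3, and the next stated calcium assessment falls when dosing ends.

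There is also a trial-conduct cost. If a high value comes to light only after assignment, the investigator must choose, without a written rule, between dosing the man and withdrawing him after randomisation. A limit applied before assignment avoids that choice.

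**Working it through.** The protocol states no figure to reproduce on this point, so the check is mainly a comparison of sections.

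**1. Can a man with high calcium be selected?** Final selection uses the screening reports and the listed criteria. The named blood tests are 25(OH)D, glucose and creatinine. The criteria diagnosed biochemically are the matching three: vitamin D deficiency, diabetes and renal insufficiency. No criterion refers to a serum calcium value, so a man who meets the rest is eligible.

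**2. Do other exclusions catch him?** Malignancy, tuberculosis, thyrotoxicosis, renal insufficiency and recent calcium use remove some men at risk. Of these, only renal insufficiency is checked in the laboratory. The others rest on history and examination, which cannot show an unrecognised high calcium value.

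**3. Is calcium measured before dosing?** By the order of the text, yes. Day 1 baseline follows assignment, and prescribing follows the list of study variables. The section on blood collection also describes an undated 5 ml draw for all intended variables, so the assay might in practice use the screening sample. No turnaround time is given.

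**4. Is the result tied to the dose?** No such rule was found. The drop rule after the dosing text concerns failure to follow the study procedure. The medical stopping rule in the walk-test section concerns symptoms during that test. The abnormality clause in Ethical Implications gives no threshold and does not mention the study drug.

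**5. When is calcium next assessed?** Day 90.

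**6. What is the regimen?** Inputs are 80,000 IU per week, 40,000 IU capsules, 90 days and 23 men in the study group.
- Weeks: 90 / 7 = 12.86, so 12 to 13 weekly doses
- Capsules per dose: 80,000 / 40,000 = 2, so 24 to 26 in all
- Total: 12 × 80,000 = 960,000 IU, to 13 × 80,000 = 1,040,000 IU
- Daily average: 80,000 / 7 = 11,429 IU

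These figures describe every man in the study group. They show what a man with high calcium would receive, not how likely or how serious harm would be.

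**7. Could a limit be applied as the variable is now written?** Not cleanly. STUDY VARIABLES gives ionic calcium in mg/ml, and the data sheet gives Ca²⁺ in mg/dl. These units differ by a factor of 100 (1 dl = 100 ml).

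**The case against.** The strongest reply is that calcium is not neglected. It is measured in all 46 men, with PTH, and on the protocol's own sequence this happens before vitamin D3 is prescribed. The three named screening assays are not the whole laboratory panel: the data sheet also has calcium, PTH, HbA1c and SGPT. A physician is responsible for medical decisions, and any abnormality detected is to be managed or referred. A laboratory reference range would supply a working threshold. The existing exclusions remove some men at risk.

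Much of this stands. A reader might infer that calcium goes unmeasured until day 90, or that following the protocol exactly means dosing a man known to have high calcium. The documents support neither reading. Calcium has a Day 1 baseline, and a physician who saw a high value would have general grounds to act.

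What remains is narrower. Measuring calcium does not oblige anyone to look at the result before the first dose, and the general clauses do not say what happens to the study drug. Even prompt review on Day 1 comes after assignment, when acting on the result means altering treatment or withdrawing a randomised man.

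**Conclusion.** The concern holds in limited form. Calcium is measured before prescribing, but it plays no part in selection, has no eligibility limit, and has no stated link to the first dose. A man with high calcium can be randomised and could be prescribed the full regimen.

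The size of the problem cannot be given. The documents do not report how common unrecognised high calcium is among such candidates, and no estimate is made here. A reader might take the total of about one million IU as the magnitude of the risk, but it is simply the planned regimen.

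The conclusion assumes that the order of the text reflects the order of events. It also assumes that no calcium rule sits in material not available for this review, namely the treatment annexure (Annexure VI) and the part of the document before the surviving data sheet. Sample size and analysis are unaffected. The change is a worthwhile, inexpensive safety improvement.

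**What to change.** Run the planned baseline calcium assay on the screening blood sample and let that value serve as the Day 1 calcium baseline. To limit extra testing, run it for men who meet all other criteria. Name the calcium fraction and use one unit throughout. Add one exclusion, applied before random assignment: serum calcium above the laboratory's upper normal limit.

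The cost is mainly wording. Because the assay is already planned for all 46 men, the only additional assays are in candidates tested and then not enrolled. That holds only if the screening value replaces the Day 1 measurement; keeping both would add one assay per enrolled man, or 46. It also assumes that the 5 ml sample is enough for the extra test. Assignment must wait for the result, and an occasional candidate will be excluded.

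This covers calcium that is high before dosing. A rise during treatment would need its own monitoring and hold rule, which this change does not supply.

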**Effect of Vitamin D3 on Lung Function and Exercise
Tolerance in D3 Deficient COPD Patients**

ClinicalTrials.gov ID: NCT03781895

Document Date: December 23, 2018

PROJECT SUMMARY

Background: Chronic Obstructive Pulmonary Disease (COPD) is a major cause of morbidity and mortality throughout the world which is a preventable as well as treatable disease. It has some important extra pulmonary effects which may contribute to the magnitude of the severity of this disease. Standard therapeutic treatment alone does not optimize its remedy. Vitamin D₃ has been found to improve the physical efficiency of patients with various morbid disorders, including respiratory ailments. **Objectives:** To evaluate the effects of Vitamin D₃ on lung functions and exercise tolerance in patients with stable moderate COPD. **Methods:** For this, a prospective interventional randomized double blinded study will be carried out on 46 (eighty) vitamin D₃ deficient (serum 25 dihydroxycholecalciferol less than 30 ng/ml), male, stable (diagnosed patient, who has not experienced any acute exacerbation, hospitalizations, urgent care visits, or changes in routine medication within 4 weeks prior to study), moderate (post bronchodilator FEV₁/FVC < 0.70 of predicted value and FEV₁ = 50 to 79% of predicted value) COPD patients (age ≥ 40 years), who will be selected from the Out Patient Department (OPD) of the National Institute of Diseases of Chest and Hospital (NIDCH) and will be grouped as A (control) and B (study) groups, respectively. All the patients will be again designated as A0, A90 (with placebo) and B0, B90 (with D₃) for before and after 90 days of follow up. All the participants will be matched in terms of duration of COPD, history of smoking, occupation and socioeconomic status. Along with the standard pharmacological treatment of COPD, the patients of the 'Study group' will be prescribed for 80000 IU of oral vitamin D₃ per week for consecutive 3 months. Along with this, all patients both the groups will be advised to continue ad lib (according to their own choice) diet. At the very 1st day of the study, the lung functions will be assessed by measuring Forced vital capacity (FVC), Forced expiratory volume in one second (FEV₁), Forced expiratory ratio (FEV₁/FVC%), Peak expiratory flow rate (PEFR) and Forced mid expiratory flow of FVC (FEF_{25-75%}), with a portable digital spirometer. In addition, exercise tolerance will be assessed by change in 6 Minute Walk Distance (6MWD) in 6 Minute Walk Test (6MWT). Changes in peripheral capillary oxygen saturation (SpO₂) by Pulse Oximeter and degree of dyspnoea by Modified Borg Scale (MBS) will also be measured both before and after 6MWT to evaluate their change in both the groups. All these variables will be measured again after 90 days standard pharmacological treatment of COPD with D₃ intervention (B group) and also without D₃ intervention (A group). For statistical analysis, Chi-square test, independent sample 't' test between two groups, paired

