Alternate: Vitamin D₃ administration improves lung function and exercise tolerance in vitamin D₃ deficient stable COPD patients.

Objectives:

General Objective

To evaluate the effects of vitamin D₃ administration on lung functions and exercise tolerance in vitamin D₃ deficient male patients with stable COPD.

Specific Objectives

[figure not shown]
- To measure the FVC, FEV₁, FEV₁/FVC%, PEF and FEF_{25-75%} of vitamin D₃ insufficient male patients with stable moderate COPD, in order to assess their lung function status.
- To measure the SpO₂ at rest, in order to assess the basal oxygenation status in this group of patients.
- To determine level of dyspnea at rest, in order to assess the basal breathlessness level in the same group of patients
- To measure the 6MWD of all the patients, in order to assess their functional exercise capacity.
- To measure both the SpO₂ and level of dyspnea again after 6MWT, for the assessment of their exercise tolerance.
- To measure all these variables after 90 days standard pharmacological treatment with vitamin D₃ and also without vitamin D₃ in stable COPD patients.
- To compare the results of baseline and endline.

Methodology:

Consolidated Standard of Reporting Trials:

(Moher et al 2010)

CONSORT 2010 Flow Diagram

TYPE OF STUDY : Prospective interventional randomized double blinded study

PLACE OF STUDY : Department of Physiology, Bangabandhu Sheikh Mujib Medical University (BSMMU), Shahbagh, Dhaka

STUDY PERIOD : March 2017 to February 2018

STUDY POPULATION : Stable, moderate COPD patients with vitamin D₃ deficiency.

SAMPLE SIZE : 46

SAMPLING : Simple random sampling .

GROUPING OF THE SUBJECTS :

Group A : 23 D₃ deficient COPD patients without D₃ administration
(Control group)

A0 : On day 0

A90 : On day 90

Group B : 23 D₃ deficient COPD patients with D₃ administration
(Study group)

B0 : On day 0

B90 : On day 90

Subject Selection:

Inclusion Criteria

- Age: >40 years (Heideri 2015)
- Socioeconomic condition: Middle class (Martineau et al 2015)
- Smoking status: (Janssens et al 2010)
 - Current smoker = with history of active smoking
 - Ex-smoker = with history of 0 – 8 quit year
 - Duration = for >30 pack years
- BMI: 25 – 29.9 kg/meter-sq (Janssens et al 2010)
- COPD patients at moderate stage according to GOLD criteria with > 4 years duration (Rees et al 2013)
- Stable COPD patients (Mehrparver et al 2010)
- Vitamin D₃ deficient: 30 ng/ml (Vitamin D Council 2017)

Exclusion Criteria

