All the above mentioned variables will be similar ,statistically non significant in both the groups to ensure the minimization of their effects.

VITAMIN ADMINISTRATION :

Collection:

Vitamin D3

Ingredient

- Cholecalciferol (40,000IU)
- Microcrystalline Cellulose (58.1 gm)
- Butylated Hydroxy Toluene (0.2mg)
- Magnesium Stearate (3mg)
 - Gelatin Capsule Shell (1mg)

Dose : 80,000 IU/wk

Route : Oral

Placebo : Courtesy of Beximco Pharmaceuticals Limited Bangladesh

Ingredient : • Microcrystalline Cellulose (303.8gm) • Butylated Hydroxy Toluene (0.2mg)

- Magnesium Stearate (3mg)
- Gelatin Capsule Shell (1mg)

STUDY VARIABLES:

(1) Spirometric variables

- FVC (L) : Forced Vital Capacity
- FEV₁ (L) : Forced Expiratory Volume in 1st second
- FEV₁/FVC Ratio (%) : Forced Expiratory Ratio
- PEF_R (L/min) : Peak Expiratory Flow Rate
- FEF₂₅₋₇₅ (L/S) : Forced Expiratory Flow in the middle of FVC

(2) Oxygenation variables

- Resting SpO₂ (%) : Resting Peripheral Capillary Oxygen saturation

(3) Exercise tolerance variables

- 6MWD (meter) : Six Minute Walk Distance
- Level of Dyspnea : Modified Borg Scale

(4) Hematological variables

- 25(OH)D (ng/ml) : 25-hydroxycholecalciferol
- PTH (pmol/l) : Parathyroid hormone
- Ca²⁺ (mg/ml) : Ionic calcium
- PO₄³⁻ (mg/ml) : Ionic phosphate
- AP (U/L) : Alkaline Phosphatase

Subsequently a standard therapeutic treatment (according to GOLD guideline) (Annexure - VI) will be prescribed to all the selected stable moderate COPD patients. In addition, the patients of

the 'Study group' will be prescribed for 80000 IU of oral vitamin D₃ per week for consecutive 90 days . Along with this, all the patients of both the groups will be advised to continue ad lib (according to their own choice) diet.

Proper education will be given about drug , method of taking medication and medication plan. Afterwards, a good rapport will be built up to take time to time follow up over telephone and visiting patient's place . Schedule appointment , hotline and follow up will be maintained properly. They will be requested to attend the Department of Physiology again on the 90th day, to have the assessment of all the above-mentioned study variables

Any patient, who failed to follow the study procedure exactly during study period, will be dropped and a new one will be included to fulfill the desired total sample number. That's why extended sample should be taken to fulfill the total sample number.

Collection of blood sample (Afroza 2015):

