The 6MWT will be performed at indoors, along a long, flat, straight, enclosed corridor with a hard surface that is seldom traveled. The walking course will be 30 meter in length which will be marked every 3 meter. The turnaround points will be marked with a cone. A starting line, which marked

the beginning and end of each 60 meter lap, will be marked on the floor using brightly colored tape.

The subject will be asked to walk at his own maximal pace along the corridor from the end, covering as much ground as he can, during the allotted time, without running. He will be also advised to take rest if he will be too exhausted to continue the test. Standard phrases at regular intervals (every 60 seconds) will be used, like: “you are doing well,” “keep up the good work”. At the same time he will be also informed about the past time and how much has left before the test was completed.

If any of the subjects developed chest pain, intolerable dyspnoea, leg cramps, staggering, diaphoresis or pale appearance the test will be immediately stopped and the subject will be dropped. Again, when any subject will complete the total study procedure (according to the exact study design), he will be congratulated for good effort.

STATISTICAL ANALYSIS:

The results will be expressed as mean with standard deviation (mean \pm SD).

The data will be statistically analyzed by a computer with SPSS (Version 16.0) using Chi-square test,(to know the qualitative difference between the observed and expected result).Spirometric variables, oxygenation variables, exercise tolerance variables and hematological variables will be found between two groups of patients. If the variables are normally distributed , statistical analysis will be done by parametric statistical test. But if it is not normally distributed then it will be transformed into natural logarithm and again into anti logarithm, to make it normally distributed, then parametric statistical test will be done. Independent sample ‘t’ test between two groups, paired Student’s ‘t’ test within two specific measurements of different durations of each group will be done.

In the interpretation of results, ≤ 0.05 level of probability (p) will be accepted as significant.

PUBLICATION POLICY

- ❖ Scientific article to be published in a scientific journal.
- ❖ Presentation in scientific seminar or conference orally or through poster presentation.
- ❖ Website dissemination through internet version of JBSP.

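### The between-arm spirometry test is not said to use any baseline value, although the plan as written measures spirometry twice before treatment

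*Combined protocol and SAP*

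**What the plan says.** STUDY PROCEDURE sets out a sequence. On the examination day blood is taken for 25(OH)D, glucose and creatinine, and then "After that his height and weight will be measured and the spirometric lung function test will be done by using a portable spirometer". Next, "After getting all the biochemical and spirometric reports the final selection will be done, according to the inclusion and exclusion criteria". Eligible patients are randomised, and only then comes the baseline: "Then the patients will be examined for the baseline value of all the study variables in Day 1". The list under STUDY VARIABLES includes five spirometric measures (FVC, FEV1, FEV1/FVC, PEFR, FEF25-75). Therapy is described after that list, opening with "Subsequently a standard therapeutic treatment (according to GOLD guideline". On this reading both sessions precede treatment, and nothing in the text gives the first session any use beyond eligibility.

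Other sections describe the timing differently. The PROJECT SUMMARY mentions one pre-treatment assessment: "At the very 1st day of the study, the lung functions will be assessed by measuring Forced vital capacity (FVC". GROUPING OF THE SUBJECTS and the data sheet call the baseline day 0, not Day 1.

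STATISTICAL ANALYSIS plans a paired t test "within two specific measurements of different durations of each group will be done" and an independent-sample t test between the two groups. It does not say what quantity the independent test compares, and it contains no baseline adjustment.

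**The concern.** The paired tests need a baseline, but they compare each arm with itself. The effect of vitamin D3 is estimated by the between-arm comparison, and that test may use no baseline at all. Spirometric values usually differ more between patients than within a patient over time, so a day-90-only comparison carries between-patient variation that earlier measurements could remove. The plan, read plainly, collects two such measurements per patient and commits neither to this test.

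What is at stake is power in a trial of 46 patients, for five of the eight non-laboratory study variables. Validity is not affected.

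**Working it through.** **Inputs from the document.** Total size: "SAMPLE SIZE : 46", 23 per group. Significance: 0.05 ("level of probability (p) will be accepted as significant"), with sidedness not given; two-sided is assumed here. Eligibility (PROJECT SUMMARY): post-bronchodilator FEV1 of 50 to 79% of predicted and 25(OH)D below 30 ng/ml. The figure of 46 cannot be reproduced, because no effect size, SD, power or formula accompanies it. For context, 23 per arm gives 80% power for a standardised difference of (1.960 + 0.842) × √(2/23) ≈ 0.83.

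**Assumptions.** The document gives no correlations. Let r be the correlation of either pre-treatment value with the day-90 value, and r0 the correlation between the two pre-treatment values. Variances are taken as equal and scaled to 1.

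**Step 1: what each analysis leaves unexplained.**
- t test on day-90 values: 1. A baseline, or a second baseline, plays no part.
- ANCOVA on Day 1: 1 − r².
- ANCOVA on Day 1 and screening as separate covariates: 1 − 2r²/(1 + r0).

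**Step 2: before allowing for selection.**

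| r | r0 | Day 1 only | Both | Reduction from Day 1 | Further reduction from screening |
|---|---|---|---|---|---|
| 0.8 | 0.8 | 0.360 | 0.289 | 64% | 20% |
| 0.8 | 0.9 | 0.360 | 0.326 | 64% | 9% |
| 0.9 | 0.9 | 0.190 | 0.147 | 81% | 22% |
| 0.9 | 0.98 | 0.190 | 0.182 | 81% | 4% |

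The rows with r0 = r are the favourable ones. They suppose that two sessions held before treatment correlate no better than sessions 90 days apart.

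Power for an assumed true difference of 0.3 SD, with r = r0 = 0.8: 17% for the day-90-only test, 40% adjusting for Day 1, 47% adjusting for both. With r = r0 = 0.9: 17%, 65% and 76%.

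**Step 3: after allowing for selection.** Screening FEV1 decides who enters, which narrows the range of all three values. Simulating FEV1 as percent predicted (assumed SD 15, mean 55 to 65, screening value kept between 50 and 80) gives:

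| r | r0 | Reduction from Day 1 | Further reduction from screening |
|---|---|---|---|
| 0.8 | 0.8 | 39–40% | 11–12% |
| 0.8 | 0.9 | 35–36% | about 6.5% |
| 0.9 | 0.9 | 57–59% | about 16% |
| 0.9 | 0.98 | 54–56% | about 4% |
| 0.95 | 0.95 | 73–74% | about 20% |

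Here r and r0 are the correlations before selection. If 0.8 is instead the correlation among enrolled patients, the 64% of Step 2 stands.

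**Step 4: cost of the extra covariate.** Residual degrees of freedom go from 43 to 42. Chance imbalance in k covariates inflates the variance on average by about (N − 3)/(N − 3 − k). That is 43/42 for one and 43/41 for two, a ratio of 42/41, or about 2.4%. A 4% gain therefore nets about 2% (0.96 × 1.024 ≈ 0.98). A 20% gain nets about 18% (0.80 × 1.024 ≈ 0.82).

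**Step 5: why not average the two values.** In the same simulation with r0 = r between 0.8 and 0.95, using the mean of screening and Day 1 as baseline shifts the within-group mean change by 0 to −0.7 percentage points through regression to the mean. Day 1 alone gives essentially no shift. For a between-arm ANCOVA the mean and the two separate covariates gave the same residual variance, so separate entry loses nothing there.

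**The case against.** **A single baseline taken after screening is a legitimate choice.** This stands. The screening session selects patients, so keeping it out of the baseline protects the paired tests from regression to the mean. For 25(OH)D the selection is one-sided, so averaging would tend to create an apparent rise in both arms. Day 1 should therefore remain the baseline within groups. Between arms, randomisation balances the selection effect, so screening is safe as a covariate.

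**The two sessions may be one.** The summary's first-day wording and the day 0 labels leave this open. The surviving part of the spirometry form has lost its column headings, so it cannot be confirmed that both values are recorded. The procedure section still reads as two sessions. If they prove to be one, adjustment for that single value keeps most of the benefit.

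**Bronchodilator state may differ.** Eligibility uses post-bronchodilator values, and the Day 1 state is not given. This is a further reason for separate covariates instead of a mean.

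**A stronger reading is tempting.** A reader might infer that baseline noise enters every spirometric comparison and that averaging the two sessions would cut variance by 25%, as if 46 patients were about 61 (46/0.75), at no cost. The document does not support this. The phrase about two measurements belongs to the paired test only. If the independent t test compares day-90 values, a second baseline changes nothing in it. The 25% applies to change scores and requires r0 = r; with r = 0.8 and r0 = 0.9 it falls to 12.5%, and with r = 0.9 and r0 = 0.98 to 5%. Averaging also has the within-group cost shown above.

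**Conclusion.** The point holds as a minor efficiency improvement. The plan does not commit the between-arm spirometry test to any baseline, and read plainly it has two pre-treatment values available for it. Most of the gain comes from adjusting for Day 1: about 64% of variance at r = 0.8 among enrolled patients, or about 35% to 40% if 0.8 is the correlation before selection. The screening value adds roughly 4% to 20% after selection, less about 2 percentage points for the extra covariate, so at the low end it is nearly neutral.

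These sizes rest on assumed correlations and, for the selection step, on an assumed FEV1 distribution. They also take a day-90-only test as the comparator; if changes were intended, the gain from Day 1 adjustment is smaller (0.40 to 0.36 at r = 0.8, or 10%, before selection). The point covers the five spirometric variables, and 25(OH)D if it is drawn on both days. It does not cover 6MWD, SpO2 or the Borg score, for which no screening measurement is described.

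**What to change.** In STATISTICAL ANALYSIS:

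1. Compare the arms on each day-90 spirometric variable by ANCOVA, with the Day 1 value as covariate and the screening value as a second, separate covariate. Do the same for 25(OH)D if it is drawn on both days.
2. Keep Day 1 alone as the baseline for the within-group paired tests, and report an ANCOVA on Day 1 only as a sensitivity analysis.
3. State whether the examination-day and Day 1 spirometry are separate sessions, and in what bronchodilator state each is done. Use one label in place of day 0, Day 1 and the first day of the study. If there is only one session, adjust for that single value.

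The cost is a few sentences, entry of the screening values, and one further degree of freedom per model. It needs no new visit, test or patient.
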